7.6 Analysis of Surveillance Results

Analysis and reporting used for annual reports and application for use result evaluation will be performed per the *Yakushokukisanhatsu* Notification No. 1121-44 (November 21, 2014), “Handling of Use Result Evaluation Concerning Marketing Approval of Medical Devices and In-vitro Diagnostic Drugs”. Subgroup analysis may be performed as required for demonstrating the safety and efficacy, and the results will be included in the surveillance result overview of the application for use result evaluation. Adverse events other than death/MI/scaffold thrombosis will be adjudicated by Surveillance Sites.

The following populations will be used for clinical evaluation:

- Intent-to-Treat [REDACTED]
- Full Analysis Set [REDACTED]
- Absorb Only Population [REDACTED]

Sub-group analysis includes the following but not limited to:

- Sex
- Diabetes
- Stent diameter

8. PUBLICATION POLICY

[figure not shown]
The Sponsor shall have the right to access and use all data and results generated during the Surveillance. The publication and/or presentation of results from a single Surveillance Site are not allowed until publication and/or presentation of the multi-center results. The Sponsor acknowledges that the Surveillance’s Principal Investigator intends to publish a multi-center publication regarding the Surveillance results. The Sponsor must receive any proposed publication and/or presentation materials at least 60 days prior to the proposed date of the presentation or the initial submission of the proposed publication in order for the materials to be reviewed by the Sponsor in compliance with the Sponsor’s publication policy. Prior approval from the Principal Investigator and the Sponsor is required for a live use or case reporting at Sites.

[figure not shown]
Among the data obtained in the Surveillance, the data that are included in the JPCI Registry will periodically be transferred to the JPCI Registry Database. Therefore, use of these data only will be an exception to the policy above.

[figure not shown]
9. DEFINITIONS

[figure not shown]
Definitions in the Surveillance are shown in Attachment 2.

ATTACHMENT 2: DEFINITION IN THE SURVEILLANCE**Scaffold/Stent Thrombosis**

The definition of ARC will be used. The scaffold thrombosis image-review committee will adjudicate scaffold/stent thrombosis reported from the Surveillance Site based on this definition.

Scaffold/Stent thrombosis should be reported as a cumulative value at the different time points and with the different separate time points. Time 0 is defined as the time point after the guiding catheter has been removed and the subject left the catheterization lab.

- **Timing:**

- Acute scaffold/stent thrombosis*: 0 - 24 hours post stent implantation
- Subacute scaffold/stent thrombosis*: >24 hours - 30 days post stent implantation
- Late scaffold/stent thrombosis†: 30 days - 1 year post stent implantation
- Very late scaffold/stent thrombosis†: >1 year post stent implantation

*Acute/subacute can also be replaced by early scaffold/stent thrombosis. Early scaffold/stent thrombosis (0 - 30 days) - this definition is currently used in the community.

†Including “primary” as well as “secondary” late scaffold/stent thrombosis; “secondary” late scaffold/stent thrombosis is a scaffold/stent thrombosis after a target segment revascularization.

- **Categories:**

- Definite
- Probable

Definitions of each category are as follows.

- **Definite scaffold/stent thrombosis**

Definite scaffold/stent thrombosis is considered to have occurred by either angiographic or pathologic confirmation.

Angiographic confirmation of scaffold/stent thrombosis*

The presence of a thrombus† that originates in the scaffold/stent or in the segment 5 mm proximal or distal to the scaffold/stent and presence of at least one of the following criteria within a 48-hour time window:

- Acute onset of ischemic symptoms at rest
- New ischemic ECG changes that suggest acute ischemia
- Typical elevation or depression in cardiac biomarkers (refer to definition of spontaneous MI)

- Nonocclusive thrombosis
 - Intracoronary thrombus is defined as a (spheric, ovoid, or irregular) noncalcified filling defect or lucency surrounded by contrast material (on 3 sides or within a coronary stenosis) seen in multiple projections, or persistence of contrast material within the lumen, or a visible embolization of intraluminal material downstream.
- Occlusive thrombus
 - TIMI 0 or TIMI 1 in- scaffold/stent or proximal to a scaffold/stent up to the most adjacent proximal side branch or main branch (if originates from the side branch).

*The incidental angiographic documentation of stent occlusion in the absence of clinical signs or symptoms is not considered a confirmed stent thrombosis.

†Intracoronary thrombus.

Pathological confirmation

Evidence of recent thrombus within the scaffold/stent determined at autopsy or via examination of tissue retrieved following thrombectomy.

• Probable scaffold/stent thrombosis

Either of the following occurred after scaffold/stent implantation will be considered a probable scaffold/stent thrombosis:

- Any unexplained death within the first 30 days‡
- Irrespective of the time after the index procedure, any MI that is related to documented acute ischemia in the territory of the implanted stent without angiographic confirmation of stent thrombosis and in the absence of any other obvious cause

‡For studies with ST-elevation MI population, one may consider the exclusion of unexplained death within 30 days as evidence of probable stent thrombosis.

For the Surveillance, the principal definition of scaffold/stent thrombosis will be ARC definite or probable scaffold/stent thrombosis.

Death (Per ARC Circulation 2007; 115: 2344-2351)

CEC will adjudicate deaths based on ARC definition.

The deaths in the Surveillance will be adjudicated per the ARC definition. All deaths are considered cardiac unless an unequivocal non-cardiac cause can be established. Specifically, any unexpected death even in

patients with coexisting potentially fatal non-cardiac disease (e.g. cancer, infection) should be classified as cardiac.

- **Cardiac death:**

Any death due to proximate cardiac cause (e.g. MI, low-output failure, fatal arrhythmia), unwitnessed death and death of unknown cause, all study procedure related deaths including those related to concomitant treatment.

- **Vascular death:**

Death due to non-coronary vascular causes such as cerebrovascular disease, pulmonary embolism, ruptured aortic aneurysm, dissecting aneurysm, or other vascular cause.

- **Non-cardiovascular death:**

Any death not covered by the above definitions such as death caused by infection, malignancy, sepsis, pulmonary causes, accident, suicide, or trauma.

Myocardial Infarction

CEC will adjudicate myocardial infarction.

ECG assessment

- **Q wave MI (Q-MI)**

Development of new, pathological Q wave on the ECG in ≥ 2 contiguous leads.

- **Non-Q wave MI (NQ-MI)**

Not categorized as Q-MI but increasing biomarkers.

Biomarker assessment

If CK-MB is measured by Site-standards, the definition used in Absorb Japan clinical trial will be used. For other cases, use the Modified WHO definition.

Definition used in the Absorb Japan clinical trial
Classification and criteria of NQMI

Classification	Biomarker Criteria	Additional Criteria
Periprocedural PCI (≤48h post-PCI)	CK-MB >5 x URL	Baseline value* < URL
Periprocedural CABG (≤48h post-CABG)	CK-MB >10 x URL	Baseline value < URL, and any of the following: New pathologic Q waves** or LBBB; new native or graft vessel occlusion; imaging evidence of loss of viable myocardium
Spontaneous All late events that are not associated with a revascularization procedure will be considered simply as spontaneous.	CK-MB > URL, or Troponin*** > URL	One or more of the following must also be present: (a) symptoms of ischemia; (b) development of pathological Q waves** (c) ECG changes indicative of new ischemia - (new ST-T changes or new LBBB), (d) or imaging evidence of a new loss of viable myocardium or a new regional wall motion abnormality
Reinfarction (not related to procedure)	If the CK and CK-MB values are stable or decreasing on 2 samples, a 25% or greater increase 3 to 12 hours after second sample is required to diagnose recurrent MI.	If biomarkers are increasing or peak not reached then insufficient data to diagnose recurrent MI.

URL=Upper Reference Limit
 LBBB=Left Bundle-branch Block
 * Baseline biomarker value is required before study procedure and presumes a typical rise and fall post
 ** If abnormal Q-wave is observed, then adjudicated as Q-MI
 *** If both values are obtained, then CK-MB must be used for adjudication

Modified WHO definition

Elevation of CK > 2 x URL and CK-MB > URL without abnormal Q-wave.

Myocardial infarction - Relation to the Target Vessel

All infarcts that cannot be clearly attributed to a vessel other than the target vessel will be considered related to the target vessel.

Revascularization

The revascularizations in the Surveillance will be adjudicated by Sites per the ARC definition.

- **Location of Revascularization:**

- **Target Lesion Revascularization (TLR)**

TLR is defined as any repeat percutaneous intervention of the target lesion or bypass surgery of the target vessel performed for restenosis or other complication of the target lesion. All TLR should be classified prospectively as clinically indicated or not clinically indicated by the investigator prior to repeat angiography. An independent angiographic core laboratory should verify that the severity of percent diameter stenosis meets requirements for clinical indication and will overrule in cases where investigator reports are not in agreement. The target lesion is defined as the treated segment from 5 mm proximal to the stent and to 5 mm distal to the scaffold/stent.

- **Target Vessel Revascularization (TVR)**

TVR is defined as any repeat percutaneous intervention or surgical bypass of any segment of the target vessel. The target vessel is defined as the entire major coronary vessel proximal and distal to the target lesion which includes upstream and downstream branches and the target lesion itself.

- **Non Target Lesion Revascularization (Non-TLR)**

Any revascularization in the target vessel for a lesion other than the target lesion is considered a non-TLR.

- **Non Target Vessel Revascularization (Non-TV)**

Revascularization of the vessel identified and treated as the non-target vessel at the time of the index procedure.

- **Non Treated Vessel Revascularization**

Revascularization of the vessel that is not treated at the time of the index procedure.

Note: TLR and TVR will be adjudicated by the angiographic core laboratory.

- **Ischemia-driven Revascularization (ID-TLR/TVR)**

- A revascularization is considered ischemia-driven if associated with any of the following:

- Positive functional ischemia study including positive FFR
- Ischemic symptoms and angiographic diameter stenosis $\geq 50\%$ by core laboratory QCA
- Angiographic diameter stenosis $\geq 70\%$ by core laboratory QCA without angina or positive functional study

Other definitions

Other definitions are based on the latest J-PCI definition.

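### The fallback MI definition, meant for cases without routine CK-MB, itself requires CK-MB and has no troponin criterion, so the same spontaneous event can be an MI at one site and not at another

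*Protocol*

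**What the plan says.** The rule is in the Protocol, Attachment 2, Myocardial Infarction, under Biomarker assessment. It has two branches:

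- "If CK-MB is measured by Site-standards, the definition used in Absorb Japan clinical trial will be used".
- "For other cases, use the Modified WHO definition".

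The first branch leads to the table of non-Q-wave MI criteria from the Absorb Japan trial. Its spontaneous row applies as follows: "All late events that are not associated with a revascularization procedure will be considered simply as spontaneous". The biomarker criterion there is "CK-MB > URL, or Troponin* > URL", and at least one further sign is needed (ischemic symptoms, Q waves, new ischemic ECG changes or imaging evidence). A footnote ranks the two markers: "If both values are obtained, then CK-MB must be used for adjudication".

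The second branch is a single line: "Elevation of CK > 2 x URL and CK-MB > URL without abnormal Q-wave".

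The ECG assessment just above describes non-Q-wave MI as "Not categorized as Q-MI but increasing biomarkers", without naming a marker or threshold. On who decides, the attachment says "CEC will adjudicate myocardial infarction".

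**The concern.** The fallback exists for cases in which CK-MB is not part of the site's standard, yet it cannot be met without a CK-MB value. The only troponin criterion for MI sits in the other branch. The spontaneous row and its footnote show that the sponsor accepts troponin when CK-MB is absent, but the routing sentence can keep an event from reaching that row.

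The same clinical event could therefore be classified differently because of laboratory routine alone, in a surveillance that may use up to 200 sites. MI is a component endpoint (Protocol 6.2.1; SAP 1.3.2.1) and enters all five composites, four as any MI and one (TLF) as target-vessel MI. A composite changes only if the MI is the patient's sole qualifying event.

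**Working it through.** The documents give no figure to reproduce; the check is to follow one type of event through the rule.

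**Event followed.** Spontaneous, no new Q wave, at least one of the further ischemia signs present, troponin above URL, CK-MB not measured. CK may be unmeasured, not above 2 x URL, or above 2 x URL, which gives three variants.

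**Criteria applied.**
- Absorb Japan spontaneous row: met if CK-MB > URL or, with no CK-MB value, troponin > URL, plus one further sign.
- Modified WHO: met only if CK > 2 x URL and CK-MB > URL.

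| Reading of the routing sentence | Type of site | Definition reached | Variants that qualify as MI |
|---|---|---|---|
| By site | CK-MB routine | Absorb Japan | 3 of 3, through troponin |
| By site | CK-MB not routine | Modified WHO | 0 of 3 |
| By event | CK-MB routine | Modified WHO | 0 of 3 |
| By event | CK-MB not routine | Modified WHO | 0 of 3 |

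These counts show the logic only. They are not weighted by how often each variant occurs and do not measure impact.

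**Which reading is likelier.** The reference to site standards suggests a property of the site; the reference to other cases suggests the event. Under the event reading, the Absorb Japan table is reached only when CK-MB was measured, and the footnote then makes CK-MB decide, so the troponin alternative in the spontaneous row would never be used. Under the site reading both definitions have a use. That favours the site reading but does not prove it, since a table carried over from another trial can contain an idle term.

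**Effect on the rate.** SAP 2.1.2 describes the denominator for the death/MI/revascularization composite as subjects with the event plus subjects without it who were followed through the time point. A followed patient whose event meets no MI definition most naturally stays in as a non-event. The spontaneous row would have counted the same patient as an event. For these events the numerator can therefore only be too small. Each such patient is 1/2,000 = 0.05 percentage points if all 2,000 are evaluable. That is a unit of scale, not an estimate.

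**How many.** The documents do not give the share of sites without routine CK-MB or the share of suspected MIs with troponin only. No visible text requires CK-MB at a suspected MI, and pre-procedural laboratory tests are recorded if done (Protocol 5.1). The number cannot be computed and may be zero.

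**Outside the point.** Q-wave MI does not depend on this rule. The periprocedural and reinfarction rows have no troponin criterion.

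**The case against.** The best reply is that an event failing a CK and CK-MB definition is simply not an MI under that definition, and that a fallback without troponin may be deliberate. The clinical events committee adjudicates every suspected MI, its charter is not among the documents, and the text of SAP 2.4 on missing data is not visible. The definition of definite thrombosis refers to a single definition of spontaneous MI, which hints that the spontaneous row was meant to apply generally.

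Part of this stands: size is not shown, and the committee may already use the spontaneous row. But the stated rule does not say so. The loose non-Q-wave wording in the ECG assessment supplies no criterion, and a missing-data rule would not normally settle which MI definition applies.

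A reader might infer four stronger things that the documents do not support:

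- That every troponin-only event is lost. This holds only on the event reading.
- That Modified WHO can never be met. It can on the site reading, and also on an event reading that treats CK-MB drawn outside the site's standard as another case. The event followed above still fails on that reading.
- That affected patients leave the denominator. This needs the explanatory sentence in SAP 2.1.2 to be read as a separate evaluability rule, which is the less natural reading.
- That the primary thrombosis criterion (at most 18 of 2,000 patients, 0.9%) is affected. The only route is the MI limb of probable thrombosis, and only if the image-review committee applies this routing. That committee works from the ARC definition, while the clinical events committee adjudicates MI. Definite thrombosis can be supported by symptoms or ECG changes without a biomarker.

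**Conclusion.** The gap in the text is real and no visible section closes it. On the likelier site reading it affects spontaneous non-Q-wave events with raised troponin, an ischemia sign and no CK-MB, at sites without routine CK-MB; on the event reading it affects such events at every site.

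The direction for these events, too few MIs relative to the sponsor's own spontaneous row, rests on one assumption: that a followed patient meeting no definition is counted as having no MI. The number is unknown and possibly zero. MI is a descriptive, non-primary endpoint in a single-arm surveillance, and the visible text sets no threshold or test on it. Severity: minor.

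**What to change.** In Attachment 2:

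1. State whether routing is by site or by event.
2. Apply the existing spontaneous row (CK-MB > URL, or troponin > URL when CK-MB was not obtained, plus a further sign) to all spontaneous non-Q-wave events at all sites. Keep Modified WHO only for other event types.
3. Report the number of suspected MIs that lack the required markers, for example those with CK only, and check their handling against SAP 2.1.2 and 2.4.

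A narrower patch, sending only troponin-without-CK-MB events to the spontaneous row, would create a new inconsistency. At a site without routine CK-MB, a patient with troponin alone would count, while one with raised troponin, raised CK-MB and CK at 1.5 x URL would go to Modified WHO and fail, because 1.5 is below the required 2. Under the wording proposed here both count.

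The cost is about two sentences and one reported count; no new threshold is introduced. There are three downsides. The reported MI rate may rise slightly. At sites without routine CK-MB, spontaneous events with CK-MB > URL but CK not above 2 x URL would now count. Some events will be judged on troponin and others on CK-MB, which the sponsor's table already allows.

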## 1. SYNOPSIS OF STUDY DESIGN AND PROCEDURES

### 1.1 Purpose of the Statistical Analysis Plan

This statistical analysis plan (SAP) is intended to provide a detailed and comprehensive description of the planned methodology and analysis to be used for Protocol 16-310, the Absorb GT1 Post-marketing surveillance study (hereinafter referred to as “Surveillance”). This plan is based on the [REDACTED] study protocol.

### 1.2 Study Objectives

The purpose of the Surveillance is to know the frequency and status of adverse device effects and adverse events in order to assure the safety of the new medical device, Absorb GT1 Bioresorbable Vascular Scaffold System ([REDACTED] hereinafter referred to as “Absorb GT1”), and to collect efficacy and safety information for evaluating clinical use results.

### 1.3 Study Design

Based on the Ministerial Ordinance on Good Post-marketing Study Practice (GPSP) for Medical Device, the Surveillance will **continuously register** approximately 2000 subjects with ischemic heart disease potentially indicated for treatment with the Absorb GT1 in two phases. **Only on-label use of the Absorb GT1 will occur** in this Surveillance until otherwise allowed by the Sponsor although this is a post-marketing surveillance.

Phase 1 will contain the first 250 registered subjects at approximately 45 sites to confirm the efficacy of physician training and to establish optimal training for increasing medical institutions participation in post-marketing evaluation. Subject will continue to register in Phase 2 at up to 200 sites until all 2000 subjects are registered in the Surveillance. The main purpose of Phase 2 is to confirm safety. Data will be collected until all subjects complete 5-year follow-up. All subjects will have a follow-up telephone contact or office visit at 3 months and 1, 2, 3, 4 and 5 years.

#### 1.3.1 Primary Endpoints

##### Phase 1 (250 subjects)

All subjects will be treated by imaging-guided implantation technique using IVUS/OCT. At least first 150 subjects will be analyzed by the core lab.

- Exclusion of very small vessels (Evaluation of RVD to exclude small vessels)
- Scaffold apposition assessed by intravascular imaging (analyzed by the IVUS/OCT core lab)

### Phase 1 + Phase 2 (2000 subjects)

- Device deficiency at procedure of implantation
- Scaffold thrombosis (ST)
  - If ST rate at 3 months is  $\leq 0.9\%$ , then commercial sale will be started
  - If ST rate at 2 years is  $\geq 1.5\%$ , then investigation will be implemented to identify the cause

Scaffold thrombosis events occurred during the Surveillance will be adjudicated by a scaffold thrombosis image-review committee.

#### **1.3.2 Other Endpoints**

To be evaluated per typical DES clinical studies.

##### **1.3.2.1 Clinical Endpoints**

Clinical endpoints will be evaluated in hospital and at each follow-up time point (3 months, and 1, 2, 3, 4, and 5 years).

- Component endpoints
  - Death (Cardiac/Vascular/Non-Cardiovascular)
  - Myocardial Infarction (TV-MI/NTV-MI)
  - Target Lesion Revascularization (ID-TLR/NID-TLR)
  - Target Vessel Revascularization (ID-TVR/NID-TVR)
  - All coronary revascularization
- Composite endpoints
  - DMR (All death/All MI/All revascularization)
  - TVF (Cardiac death/All MI/ID-TVR)
  - MACE (Cardiac death/All MI/ID-TLR)
  - TLF (Cardiac death/TV-MI/ID-TLR)
  - Cardiac death/All MI

Clinical events committee (CEC) will evaluate all deaths and suspected of MIs for 3 years maximally. Surveillance sites will cooperate in providing materials needed to adjudication (e.g., death report, discharged summary) to the Sponsor, if a patient is dead or is suspected to have MI.

### 1.3.2.2 Angiographic Endpoints (core lab analysis)

#### Pre-procedure

- Morphology
- TIMI blood flow
- Lesion length
- RVD
- MLD
- %DS

#### Post-procedure

- TIMI blood flow
- RVD (Proximal, Distal, Segment)
- MLD (Proximal, Distal, In-stent, In-segment)
- %DS (Proximal, Distal, In-stent, In-segment)
- Acute gain (In-stent, In-segment)

### 1.3.2.3 IVUS/OCT Endpoints (core lab analysis)

The IVUS/OCT endpoints will be updated according to the finalized definitions from the core labs.

#### Pre-procedure (or after pre-dilatation)

- Lumen diameter
- Lumen area

#### Post-procedure

- Lumen diameter
- Lumen area
- MLA
- Incomplete apposition of the Absorb GT1 strut (per lesion, per strut)
- Fracture of the Absorb GT1 strut

